#### 8.1.1. Calculation of the Summary Statistics

For continuous data the following rules will be applied:

- Missing values will not be imputed, unless specifically stated otherwise.
- Unrounded data will be used in the calculation of summary statistics.
- If the number of subjects with valid observations (n) <3, summary statistics will not be calculated, with the exception of n, minimum, and maximum.
- As ET data is not associated with any scheduled timepoint, it will be excluded from all calculations of summary statistics.
- Postdose repeats and unscheduled assessments will not be included in calculation of summary statistics.

For categorical data the following rules will be applied:

- If the categories of a parameter are ordered (eg, AE severity), all categories between the possible minimum and maximum categories will be included, even if n = 0 for a given category. If the categories are not ordered (eg, race), only those categories for which there is at least 1 subject represented will be included.

- Missing values will not be imputed, with the exception of AEs where the ‘worst-case’ approach will be taken (see [Section 8.6.1](#)), or unless specifically stated otherwise. A ‘missing’ category will be included for any parameter for which information is missing. This will ensure that the population size totals are consistent across different parameters.

All protocol deviations and data issues (eg missing data, out of protocol window) that occur during the study, including those related to COVID-19, will be considered prior to database lock for their severity/impact on how the data will be displayed.

### **8.1.2. Repeat and Unscheduled Readings**

For vital sign measurements and ECG data only, any predose value recorded in addition to the original value or a postdose value recorded within 15 minutes of the original value will be defined as a repeat value; any postdose value recorded more than 15 minutes after the original value will be defined as an unscheduled value. For all other data types (eg, laboratory parameters), any value recorded in addition to the original value will be defined as an unscheduled value.

The original scheduled value will be used in all calculations postdose. In the event of any repeats or unscheduled measurements taken pre-dose the values will be considered when determining the baseline value for each period.

Postdose repeats, unscheduled values, and ET measurements will be excluded from all calculations with the exception of the baseline derivation (see [Section 8.1.3](#)).

### **8.1.3. Definitions of Baseline and Change from Baseline**

Baseline value is defined as the last non missing measurement before administration of LOXO-305 on Day 1 and Day 8.

If the date/time of the value is incomplete or missing, it will be excluded from the baseline calculation, unless the incomplete date/time indicates the value was recorded prior to dosing on Day 1 and Day 8.

Individual changes from baseline will be calculated by subtracting the individual subject’s baseline value from the value at the timepoint. The mean change from baseline will be defined as the mean of the individual changes from baseline for all subjects.

See [Section 8.1.2](#) for more detail on handling repeat and unscheduled readings in the calculations.

### **8.1.4. Period Specific Study Day**

Period specific study day is defined as per Table 3 for ECG and Vital signs and Table 4 for clinical laboratory parameters.

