- e. 12-lead ECGs will be obtained at Screening and Check-in (Day -1), Day 1 (predose), Day 4 (72 hours postdose on Day 1), Day 8 (predose), Day 11 (72 hours postdose on Day 8), and Day 15 (168 hours postdose on Day 8 [EOT]) or ET. 12-lead ECGs will be collected after the subject has rested in the supjne position for at least 10 minutes. When scheduled at the same time as PK blood draws, 12-lead ECGs will be obtained prior to and as close as possible to having blood drawn. The allowed sampling window for 12-lead ECGs is ± 30 minutes from the nominal timepoint for all postdose 12-lead ECGs and no less than 10 minutes prior to dosing for predose 12-lead ECGs.
- f. Vital sign measurements (supine BP and pulse rate) will be obtained at Screening, Check-in (Day -1), Day 1 (predose, 2 hours after dosing), daily on Days 2 through 7 (24, 48, 72, 96, 120, and 144 hours postdose on Day 1), Day 8 (predose, 2 hours after dosing), daily on Days 9 through 14 (24, 48, 72, 96, 120 and 144 hours postdose on Day 8), and on Day 15 (168 hours postdose on Day 8 [EOT]) or ET. Blood pressure and pulse rate will be measured using the same arm for each reading after the subject has been supine for at least 5 minutes. When scheduled at the same time as PK blood draws, vital sign measurements should be carried out prior to and as close as possible to having blood drawn. The allowed sampling window for vital sign measurements is ± 30 minutes from the nominal timepoint for all postdose vital sign measurements and no less than 10 minutes prior to dosing for predose vital sign measurements.
- g. Respiratory rate and body temperature will be obtained at Screening, Check-in (Day -1), and Day 15 (168 hours postdose on Day 8 [EOT]) or ET.
- h. Oxygen saturation will be measured via pulse oximetry at Screening, Check-in (Day -1), predose on Day 1, and Day 15 (EOT; 168 hours postdose on Day 8) or ET. The allowed sampling window for oxygen saturation measurements is ± 30 minutes from the nominal timepoint for all postdose oxygen saturation measurements and no less than 10 minutes prior to dosing for predose oxygen saturation measurements.
- i. A HDYF? inquiry will be performed at Screening (after the ICF is signed), at Check-in (Day 1), at each postdose vital sign measurement, and at an appropriate time for all other days.

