**Table 3: ECG and Vitals Study day**

Period	Period Specific Study Day							
	Baseline	Day 1	Day 2	Day 3	Day 4	Day 5	Day 6	Day 7
1	1 (pre-dose)	1 (post dose)	2	3	4	5	6	7
2	8 (pre-dose)	8 (post dose)	9	10	11	12	13	14

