**Table 4: Clinical laboratory parameters Study day**

Period	Period Specific Study Day						
	Baseline	Day 2	Day 3	Day 4	Day 5	Day 6	Day 7
1	Day -1			4			7*
2	Day 7 Period 1			10			14

\*Day 7 measurements will be summarized at day 7 for period 1 used as baselines for the period 2.

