#### **8.6.4. 12-lead Electrocardiogram Parameters**

All 12-lead ECG parameters, with changes from baseline will be listed; any value outside the clinical reference range will be flagged, and whether the out of range value was deemed clinically significant or not clinically significant will be indicated.

The observed results and change from baseline for all 12-lead ECG parameters will be summarized descriptively by treatment and period specific timepoint. QTcF values that are  $> 450$  msec and increase from baseline  $> 30$  msec will be flagged in the data listing.

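### SAP Table 3 stops at study Day 14, so the scheduled Day 15 ECG and vital signs have no row in the by-treatment safety summaries

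*SAP*

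**What the plan says.** SAP 8.6.4 commits to ECG results and changes from baseline that "will be summarized descriptively by treatment and period specific timepoint"; SAP 8.6.3 makes the same commitment for all vital signs. The timepoint comes from SAP 8.1.4: "Period specific study day is defined as per Table 3 for ECG and Vital signs and Table 4 for clinical laboratory parameters".

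Table 3 has eight columns: Baseline and Days 1 to 7. Its Period 2 row reads "8 (pre-dose) 8 (post dose) 9 10 11 12 13 14". There is no column after Day 7 and no entry for study Day 15.

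Protocol Appendix 4 continues one day further. Footnote e places the Period 2 ECGs at "Day 8 (predose), Day 11 (72 hours postdose on Day 8), and Day 15 (168 hours postdose on Day 8 [EOT]) or ET". Footnote f ends the blood pressure and pulse schedule at "120 and 144 hours postdose on Day 8), and on Day 15 (168 hours postdose on Day 8 [EOT]) or ET". Footnotes g and h also put respiratory rate, temperature and oxygen saturation on Day 15, with no earlier post-dose reading.

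For laboratory data, the footnote to Table 4 gives one draw two roles: "Day 7 measurements will be summarized at day 7 for period 1 used as baselines for the period 2". Table 3 has no such note.

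**The concern.** A programmer who builds the summaries from Table 3 has nowhere to put a Day 15 value. The SAP promises summaries of all ECG and vital sign results, yet its own mapping omits a scheduled visit. Safety and tolerability is the secondary objective, and Day 15 is the last on-site assessment.

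At stake is the completeness of the descriptive safety tables. The latest post-dose readings of Period 2 would not be summarized under the treatment given in that period. The Day 8 predose readings would be tabulated only as the starting point for the second treatment, with no row showing them as a change after the first.

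**Working it through.** The documents give no figure to reproduce. The check converts each scheduled post-dose time to a study day and looks for a cell in Table 3.

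**Inputs.** Doses are on Days 1 and 8 (protocol 3.1). Times are from protocol Appendix 4, footnotes e to h. The cells are those of SAP Table 3.

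**Formula.** Study day = dose day + hours/24, rounded down.

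- Period 1, 168 h: 1 + 168/24 = Day 8, before the second dose.
- Period 2, 168 h: 8 + 168/24 = Day 15.

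**Mapping.**

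| Measure | Time after dose | Period 1 | Period 2 |
|---|---|---|---|
| BP, pulse | 2, 24, 48, 72, 96, 120, 144 h | Days 1–7: all have cells | Days 8–14: all have cells |
| BP, pulse | 168 h | Day 8 predose: Period 2 baseline only | Day 15: no cell |
| ECG | 72 h | Day 4: has a cell | Day 11: has a cell |
| ECG | 168 h | Day 8 predose: Period 2 baseline only | Day 15: no cell |
| Respiratory rate, temperature, oxygen saturation | 168 h | not scheduled | Day 15: no cell |

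**Counts.**

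- Unassigned sets: 20 completers × 1 Day 15 visit = 20. Protocol 8.1 gives up to 20 subjects.
- ECG by the protocol's own labels: three post-dose recordings per subject (Days 4, 11 and 15), of which 1 of 3 has no cell. The only post-dose summary time left is 72 h.
- Blood pressure and pulse, Period 2: 8 post-dose times, of which 7 have cells.
- Respiratory rate, temperature and oxygen saturation: 1 post-dose time, of which 0 have cells.
- With the added column, post-dose summary rows per period rise from 7 to 8 for blood pressure and pulse and from 1 to 2 for ECG. The other three measures gain their only row, in Period 2.

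**Does another rule exclude Day 15?** SAP 8.1.1 and 8.1.2 leave out early-termination, post-dose repeat and unscheduled values. For a subject who completes, the Day 15 reading is none of these. No other SAP rule explains its absence.

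**The case against.** Several points on the other side are sound.

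- **The results are not lost.** SAP 8.6.3 and 8.6.4 list every value with change from baseline and out-of-range flags, and QTcF flags as well. A reader might infer that the Day 15 safety data go unreported; the listings rule that out. Final scheduled laboratory tests are on Day 14, which Table 4 covers.
- **The TFL shells may add a row.** They are not among the documents. The omission follows from the SAP text and is not shown to occur in the output.
- **Day 8 predose has a cell.** The protocol labels it predose, and protocol 8.4 and SAP 8.1.3 require it as the Period 2 baseline. A reader might count 40 unassigned sets, or half of all post-dose ECGs, but only the 20 Day 15 sets lack a cell.
- **The laboratory comparison is imperfect.** No Day 8 predose laboratory draw is scheduled, so the Day 7 sample has to serve twice. ECG, blood pressure and pulse have their own Day 8 predose reading. Giving it a second role is sensible for matching rows, but its absence is a weaker point than the missing Day 15.
- **Harm to the treatment comparison is not shown.** A reader might infer that a late Period 1 effect would hide or reverse the change credited to the other treatment. No figure supports that. At the 200 mg half-life of 19.9 h in protocol Table 1 (patients, steady state, limited sampling), 168/19.9 = 8.4 half-lives, leaving about 0.3% of drug. At the 30.1 h of the 300 mg row, 168/30.1 = 5.6 half-lives, leaving about 2%. The proposed change also keeps the same Period 2 baseline.
- **Discharge review is separate.** Appendix 4 footnote t requires individual results to be available to the investigator before release, which does not depend on summary tables.

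Protocol 8.4 also asks for summaries only where possible and by timepoint as needed. That softens the protocol's requirement, but the SAP's commitment to summarize all these results by period-specific timepoint still stands and conflicts with its own table.

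**Conclusion.** The point holds as a mapping gap. SAP Table 3 omits study Day 15, so the scheduled Day 15 ECG and vital signs have no place in the by-treatment descriptive tables. That is 20 sets, assuming 20 completers and TFL shells that follow Table 3. The heaviest effect is on respiratory rate, temperature and oxygen saturation, which are left without any post-dose summary; ECG keeps only 72 h. Separately, and less seriously, the Day 8 predose ECG, blood pressure and pulse are not also presented as a 168 h result of Period 1. The equivalence to 168 h rests on the 7-day interval between doses, not on a protocol label.

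The consequence is confined to descriptive output for the secondary objective. No inferential safety analysis is planned, and the primary PK analysis is unaffected. It should still be corrected, because the rule as stated leaves out scheduled data that the SAP says it will summarize.

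**What to change.** Add a Day 8 (168 h) column to SAP Table 3:

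- Period 2 = study Day 15, with change from the Period 2 baseline.
- Period 1 = study Day 8 predose, with change from the Day 1 baseline, so that ECG, blood pressure and pulse have a matching row in both periods.
- Footnote: Day 8 predose values are summarized at 168 h for Period 1 and also remain the Period 2 baseline.

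The footnote should also name the baseline for the three measures with no scheduled Day 8 predose reading. Under SAP 8.1.3, if only scheduled readings exist, that is Check-in (Day -1) for respiratory rate and temperature and Day 1 predose for oxygen saturation.

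The cost is one column and one footnote in the SAP, with matching rows in the TFL shells. All the data are already scheduled for collection.

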**Table 3: ECG and Vitals Study day**

Period	Period Specific Study Day							
	Baseline	Day 1	Day 2	Day 3	Day 4	Day 5	Day 6	Day 7
1	1 (pre-dose)	1 (post dose)	2	3	4	5	6	7
2	8 (pre-dose)	8 (post dose)	9	10	11	12	13	14

**Table 4: Clinical laboratory parameters Study day**

Period	Period Specific Study Day						
	Baseline	Day 2	Day 3	Day 4	Day 5	Day 6	Day 7
1	Day -1			4			7*
2	Day 7 Period 1			10			14

\*Day 7 measurements will be summarized at day 7 for period 1 used as baselines for the period 2.

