5.3. Randomization

Subjects will be assigned a unique identification number upon screening. Subjects who complete the study screening assessments and meet all the eligibility criteria will be assigned a unique randomization identification number (in accordance with the requirements in Section 4.5 and the randomization scheme generated by Covance) prior to the time of the first dose, different from the screening number, and will receive the corresponding product according to the randomization scheme generated by Covance.

Subjects will receive each treatment (A and B) on one occasion. The treatments will be administered on Day 1 (Treatment A or B) and Day 8 (Treatment A or B). The sequences to be used in the randomization will be AB and BA.

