8.5. Data Handling and Record Keeping

Any changes to information in the trial progress notes and other source documents will be initialed and dated on the day the change is made by a CRU staff member authorized to make the change. Changes will be made by striking a single line through erroneous data and clearly entering the correct data (eg, wrong data right data). If the reason for the change is not apparent, a brief explanation for the change will be written adjacent to the change by the CRU staff member.

The Data Management Plan will be approved by the Sponsor.

Data will be validated during data entry by the CRU and verified by the Study Monitor. Data will then be reviewed by the data management group to resolve any outstanding issues. Listings will be generated after the database is cleaned by data management and will be reviewed by the Covance scientific team. The eCRF and ancillary data will be converted into final SAS® datasets following Study Data Tabulation Model or Sponsor-provided specifications. The final datasets structure will be verified using Web Submission Data Manager®, while the dataset content will be peer reviewed by an independent programmer.

The tables, figures, and listings (TFLs) will be programmed per the final SAP. All TFLs will be peer reviewed by an independent programmer. In addition, draft TFLs will be reviewed by the Covance scientific team during the dry run and data review meetings.

The peer review will be performed by independent programmers following the quality control process and programming checklists.

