- 1. On Day 8, LOXO-305 will be administered in the morning at approximately the same time as LOXO-305 was administered on Day 1 (+/- 15 minutes), either following a fast of at least 10 hours prior to and 4 hours after LOXO-305 administration (with water restricted for 1 hour prior to and 1 hour post-LOXO-305 administration) or approximately 30 minutes after the start of a high-fat breakfast (with water restricted for 1 hour prior to and 1 hour post-LOXO-305 administration), according to the treatment sequence the subject is randomly assigned to. High-fat breakfast should be entirely consumed within 30 minutes.

- n. Clinical chemistry panel (fasted for at least 8 hours), coagulation parameters, hematology panel, and UA will be performed at Screening, Check-in (Day -1), Day 4 (72 hours postdose on Day 1), Day 7 (144 hours postdose on Day 1), Day 11 (72 hours postdose on Day 8), and Day 14 (144 hours postdose on Day 8, if the subject completes the study [EOT]), or on the day of ET. At ET or the day before EOT (Day 14), subjects are not required to be fasted prior to clinical laboratory evaluations.
- o. Testing for COVID-19 will be conducted at a minimum at Screening and Check-in (Day -1). Testing for COVID-19 may also be conducted periodically during the subject's CRU confinement, at the discretion of the Investigator (or designee). Tests will be performed by rapid polymerase chain reaction or equivalent.
- p. Urine drug screen for drugs of abuse (including cotinine) and alcohol screen (urine or breath).

CONFIDENTIAL Protocol Reference: LOXO-BTK-20009 Covance Study: 8419688

- q. Prior and concomitant medication administration will be recorded beginning at informed consent. In addition, all Investigator-approved prescription and over-the-counter medications taken by a subject within 14 days or 5 half-lives (if known), whichever is longer, prior to Day 1 will be recorded on the subject's electronic CRF.
- r. Female subjects only. Performed at Screening, Check-in (Day -1), and Day 14 (144 hours postdose on Day 8), if the subject completes the study (EOT) or on the day of ET.
- s. Post-menopausal female subjects only.

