#### **8.6.2. Clinical Laboratory Parameters**

All clinical laboratory parameters, with changes from baseline will be listed; any value outside the clinical reference range will be flagged, and whether the out of range value was deemed clinically significant or not clinically significant will be indicated. Separate listings will be provided for any parameter for which there is any individual subject value outside the respective clinical reference range.

The observed results and change from baseline for clinical chemistry, hematology, and coagulation parameters will be summarized descriptively by treatment and period specific timepoint.

Values recorded as  $< x$ ,  $\leq x$ ,  $> x$ , or  $\geq x$  will be displayed in the listings as recorded. For the derivation of listing flags, calculation of summary statistics, and presentation in the figures,  $< x$  and  $\leq x$  values will be set to 0, whereas  $> x$  and  $\geq x$  values will be set to x.

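### SAP Table 4 places the Period 2 Day 4 laboratory results on study Day 10, but the protocol draws them on Day 11

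*SAP*

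**What the plan says.** SAP section 8.1.4 gives separate day mappings for the two groups of safety data: "Period specific study day is defined as per Table 3 for ECG and Vital signs and Table 4 for clinical laboratory parameters". In Table 4, the Period 1 row takes period-specific Days 4 and 7 from study Days 4 and 7. The Period 2 row, with its empty cells closed up, reads "Day 7 Period 1 10 14": the baseline is the Day 7 result of Period 1, Day 4 comes from study Day 10, and Day 7 from study Day 14.

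The mapping feeds SAP section 8.6.2: "The observed results and change from baseline for clinical chemistry, hematology, and coagulation parameters will be summarized descriptively by treatment and period specific timepoint".

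The protocol fixes when the blood is drawn. In Appendix 4, footnote n, the Period 2 laboratory draws are on "Day 11 (72 hours postdose on Day 8), and Day 14 (144 hours postdose on Day 8". In Period 1 they are on Day 4 (72 hours) and Day 7 (144 hours).

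**The concern.** Table 4 sends the programmer to a study day on which no laboratory sample is scheduled, and it gives no place to the day on which one is. It also pairs a 72-hour day in Period 1 with a 48-hour day in Period 2 under one Day 4 label.

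The cell is part of an operating rule. Section 8.1.4 is the only period-day mapping in the SAP, and protocol section 8.5 states: "The tables, figures, and listings (TFLs) will be programmed per the final SAP". Followed as written, the Period 2 Day 4 slot stays empty for chemistry, hematology and coagulation. The Day 4 summary then rests on Period 1 alone: Treatment A from sequence AB only, and Treatment B from sequence BA only. At that timepoint the fed and fasted columns would describe different subjects, which loses the within-subject pairing of the crossover. Safety with and without food is the secondary objective.

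**Working it through.** **Inputs.** Dosing days, protocol section 5.3: "The treatments will be administered on Day 1 (Treatment A or B) and Day 8 (Treatment A or B". Hours after the second dose, protocol Appendix 4, footnote f (vital signs): "daily on Days 9 through 14 (24, 48, 72, 96, 120 and 144 hours postdose on Day 8". Period 2 row of SAP Table 3: "8 (pre-dose) 8 (post dose) 9 10 11 12 13 14". Draw counts and volumes: protocol Appendix 3. Sample size: protocol section 8.1.

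**1. Day arithmetic.** Study day = dosing day + hours / 24.

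- Period 1: 72 h gives 1 + 3 = Day 4; 144 h gives 1 + 6 = Day 7. Both agree with Table 4.
- Period 2: 72 h gives 8 + 3 = Day 11; 144 h gives 8 + 6 = Day 14. Table 4 has 14 for the second but 10 for the first.
- Day 10 is (10 − 8) × 24 = 48 h after the second dose, which is period-specific Day 3.

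The SAP's figure of 10 is therefore not reproduced; the arithmetic gives 11.

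**2. Offsets within the SAP (Period 2 day minus Period 1 day).**

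- Table 3: 8−1, 8−1, 9−2, 10−3, 11−4, 12−5, 13−6, 14−7. The offset is 7 in all eight columns.
- Table 4: Day 7 column 14−7 = 7; Day 4 column 10−4 = 6. The Day 4 entry is the only one out of line.

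**3. Count of draws.** Appendix 3 allows six sets of clinical laboratory samples: 6 × (4 + 4 + 3) mL = 66 mL, as printed there. Footnote n uses all six for a subject who completes: Screening, Day −1, and Days 4, 7, 11 and 14. The further mark in the discharge/early termination column of the schedule is covered by the same footnote, which puts the final draw on Day 14 for completers or on the day of early termination. No Day 10 draw is left over.

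**4. Consequence if programmed literally.** The scheduled postdose days are {4, 7, 11, 14}; the Table 4 days are {4, 7, 10, 14}. Day 11 has no slot and the Day 10 slot has no data. With 20 subjects, 10 per sequence, all completing:

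- Scheduled postdose draws: 20 × 4 = 80. Unmapped: 20, which is 20/80 = 25%.
- Day 4 summary per treatment: 10 (Period 1) + 0 (Period 2) = 10 of 20 subjects.
- Day 7 summary per treatment: 10 + 10 = 20 of 20 subjects.

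**5. Other explanations.** The 10 stands in the same column as the Period 1 entry of 4; moved under Day 3, it would still point to a day without scheduled samples. A deliberate change is not declared: SAP section 10 reports no significant changes, and the history for Version 2.0 lists only the period effect added to the model. An ad hoc Day 10 sample could not fill the slot, because SAP section 8.1.1 keeps unscheduled postdose assessments out of the summary statistics.

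**The case against.** The cell itself has no good defence; the argument is about consequence. The half-empty summary arises only if the programming selects on the number 10. The column is headed Day 4, only one scheduled Period 2 draw fits it, and SAP section 8.1.2 bases postdose calculations on the original scheduled value. All of this points to Day 11. Section 8.6.2 speaks of a period-specific timepoint, and equating that with the study day of section 8.1.4 is an inference. A Day 4 row with half the count of the Day 7 row would also be conspicuous, and protocol section 8.5 provides for independent programmer review and scientific review of draft tables. Nothing is lost from the record, since SAP section 8.1 lists all captured data, and section 8.6.6 plans no inferential safety analysis.

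These points stand, and they keep the matter small. They do not make the entry right. A programmer checking output against the SAP could reproduce the same mapping faithfully, and the version marked final still carries it. The table shells, which might already show the correct day, were not available.

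**Conclusion.** The concern holds, as a minor inconsistency. That the entry should be 11 is close to certain: the dosing days, the protocol's laboratory schedule, the draw count and SAP Table 3 all agree. Whether the error would reach the final tables is much less certain.

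The figures of 25% of postdose draws unmapped and 10 of 20 subjects per treatment at Day 4 are conditional. They assume literal programming of Table 4 and 20 completers split equally between the sequences. Even then the effect stops at one descriptive laboratory timepoint. The listings, out-of-range flags, Day 7 summaries (study Days 7 and 14) and primary pharmacokinetic analysis are unaffected.

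**What to change.** In SAP Table 4, Period 2 row, change the Day 4 entry from 10 to 11. Check the analysis-dataset specification and the table shells, and make the same correction wherever they carry the entry.

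The cost is one table cell and any matching specification lines. It needs no new data and no change to study conduct.
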